4.2 Overall study design

The study consists of 2 arms, one experimental with allogeneic MSV, and another control in the to be injected into the area of the paravertebral muscles near the injury saline serum containing 1% mepivacaine (1 ml of 2% mepivacaine + 1 ml of saline) in identical volume and subject to the same maneuvers as the intervention on the arm experimental. Participants in the study will be offered the possibility of, once completed the study, receive MSV treatment if it proves beneficial and the patient so wishes. The inclusion criteria in both arms are identical, but after recruiting patients will be randomly assigned to one of the treatments. The Cell manufacturing will be carried out by Citospin at the facilities of the Park Scientist of the UVa and the application and monitoring will be carried out at the Clinical Hospital University of Valladolid. 24 patients diagnosed with low back pain and / or low back pain attributable to disc degeneration and evidence of proven continuity of the external fibrous ring in the magnetic resonance image. The patients will be evaluated clinically, by the previous imaging studies (X-ray and MRI). If they are considered inclusive, they will be provided with the information regarding the clinical trial and the "Patient Information Sheet" (Annex II), citing them for the Inclusion visit. In the "Inclusion Visit", if the patient decides to participate in the trial, they must sign the "Informed Consent Document" and a visit will be scheduled for the practice of MRI and radiographs, which will be considered the pattern on which the possible determinable changes in the controls at 6 and 12 months. If you are MRI and X-rays have been recently performed and their characteristics are valid for the study, its repetition can be avoided. In this visit, basic analytics will also be requested, serology for HIV, lues and hepatitis B and C, and a serum sample will be obtained that will be sent to the Cell Production Unit for filing in the Seroteca. Although the Positive serology is not a criterion for exclusion of the recipient in the present test, it will be performed for epidemiological and preventive purposes. At the next visit (V0), it will be verified that all the inclusion criteria persist and that no exclusion is presented and the patient will be randomized (blind for him) in one of the two treatment groups and the date of implantation of MSV (V1). Once the mobile application is made, the patients will be followed up safety and to determine efficacy as established in the visit program (V2 to V5, see later).

5. SELECTION OF PATIENTS

Patients diagnosed with low back pain and / or low back pain will be included in the clinical trial attributable to disc degeneration and evidencing the continuity of the

external fibrous ring verified by MRI. The goal is to complete 12 patients in each of the two groups.

5.1 INCLUSION AND EXCLUSION CRITERIA

5.1.1. Inclusion criteria

1. Lumbar degenerative disc disease of one or two discs with predominance of pain lumbar and / or persistent sciatica after conservative treatment (medical and physiotherapy) of more than 6 months of evolution.

2. Complete fibrous ring, capable of containing the cellular implant, demonstrated with in the MR image (Adams stages 2, 3 and 4) (Adams et al., 2000).

3. Decrease in the height of the disc space of more than 20% measured

radiographically in lateral image.

4. Absence of spinal infection.

5. Hematological and biochemical analyzes without significant alterations that contraindicate intervention

6. The patient is able to understand the nature of the study.

7. Written informed consent of the patient.

5.1.2 Exclusion criteria

1. Age under 18 years old, or over 75 years old or legally dependent

2. Allergies to gentamicin, or to bovine, bovine or equine sera.

3. Congenital or acquired diseases with significant deformations of the spinal column that make application difficult.

4. Vertebral pathology that conditions segmental instability, stenosis of the medullary canal, pathology of the isthmus and other alterations that could compromise the study at the discretion of the researchers

5. Presence of Modic III changes in the RNM images (Modic & Ross, 2007) (Annex VIII).

6. Weight overload with a body mass index (BMI) greater than 35 (obesity grade II; SEEDO), where BMI = mass in Kg / (height in m) 2

7. Pregnancy or breastfeeding

8. Neoplastic disease

9. Immunosuppressive states

10. Participation in another clinical trial or treatment with another product in phase Research in the 30 days prior to inclusion in the study.

11. Any other pathology or circumstance that compromises participation in the study according to medical criteria

5.2.1 Clinical Criterion

It includes the evaluation of the state of health and quality of life through the SF-12 questionnaire (abbreviated version of the SF-36), the evaluation of low back pain (and sciatic pain if any) using visual analog scale (VAS) and disability assessment using the index of Oswestry. They are described in detail in Annexes V, VI and VII.

5.2.2 Imaging Criterion

5.2.2.1 Radiography.

The intervertebral space decrease of more than 20% in the profile projection in comparison with healthy adjacent segments is a criterion used for the purpose of inclusion or exclusion in the trial.

The classification of degeneration by discographic criteria will be carried out according to the staging Adams (Adams et al., 1986):

1. Cotton ball. No signs of degeneration

2. Lobular. Nucleus pulposus amorphous, soft and white

3. Irregular. Mature disc, with nucleus pulposus beginning to merge and with fibrous fragments

4. Cracked. Degenerated disc, with fissures and cracks in the nucleus pulposus and in the inner part of the annulus fibrosus

5. Broken. Degenerated disc, with radial fissure that reaches the outer edge of the annulus fibrosus

A lateral x-ray in standing and flexion-extension will be taken to assess the excess of mobility in the pathological segment and its evolution during treatment.

5.2.2.2 Magnetic Resonance Imaging (MRI):

T2 and STIR (short T1 inversion recovery) sequences will be performed in the axial and sagittal. They will be carried out at the beginning and 6 and 12 months after the intervention. It will be carried out quantification of the water content of the disc on the T2 image without contrast as described in detail in section 3.3 (see Figure 4). The MRI image will also be used to assess the integrity of the external fibrous ring at the inclusion visit.

5.2.3 Laboratory Analysis

They include serological determination of hepatitis B and C, HIV, lues and obtaining a sample of serum for seroteca. Although positive serology is not a criterion for exclusion of the recipient in this trial will be carried out for epidemiological purposes. The rest of the Analysis will be carried out according to usual protocols. Additional tests will be considered when clinical or complications are suspected radiographically. In the case of marrow donors

It will be necessary to carry out HIV and hepatitis serology by PCR techniques (Nucleic Acid Amplification Technology, NAT) to maximize sensitivity and thus avoid quarantine which would otherwise be necessary (Roth, 2010), but impossible to fulfill in this case. This possibility is thus contemplated in RD 1301-2006 for cells and tissues. Would convenient, and so it has been programmed, to store a tube of serum, both from the donor and of the receiver, in the Seroteca to ensure the possibility of carrying out new analyzes before situations not contemplated or not known at the present time.

5.2.4 Pathological study

It will be carried out obligatorily in case of necessary subsequent intervention on the disc.

5.3 SELECTION OF DONORS OF MESENCHYMAL CELLS

Leftover cells from patients who undergoing autologous MSV transplantation in the trial Eudra CT2009-017405-11 that we are carrying out simultaneously or in compassionate cases authorized by the AEMPS which followed the same protocol. In the above cases often we obtain more cells than needed for their own treatment in the selection process for adhesion to plastic. Informed consent will be requested (see Annex II) to donate part of the excess cells. Alternatively, if the above procedure is not possible, donors will be recruited among healthy patients undergoing spinal or hip surgery in the Service of Traumatology of the Hospital Clínico Universitario de Valladolid and who wish and consent to donate bone marrow obtained during surgery. Consent is shown reported in Annex II.

5.3.1 Inclusion criteria:

□ Donors must meet all the criteria for the selection of blood donors and donation of hematopoietic precursors (RD 1088/2005, of September 16 by which establishes the technical requirements and minimum conditions of the hemo-donation and transfusion centers and services).

□ They must sign the informed consent.

□ They must undergo PCR serology (NAT) for HIV and hepatitis B and C and provide a serum sample for the seroteca (see details above).

5.3.2. Exclusion criteria

• Any criteria for non-compliance with the inclusion criteria

• HIV or Hepatitis positive

5.3.3 Procedure:

It is described in detail below (section 6.1). In essence, in the Eudra CT2009-017405-11 usually starts with 80-100 ml of bone marrow. The mononuclear cells and is selected by adherence to the plastic in T-175 bottles. Depending performance, which is highly variable depending on the patient, is obtained in this phase between 6 and 45x106 adherent cells, which expand about 10 times in the following 3 weeks for use in the clinical trial. Taking into account that the required number of MSV is of about 80x106 cells, in some patients there is a significant surplus of cells in this stage. It is proposed here to start between 1 and 5 additional expansion batches (depending on the number of cells obtained) for use in the present clinical trial. The details of the protocol are discussed in section 6.1.

5.4 NUMBER OF EXPECTED PATIENTS AND RATIONALE

As it is a phase I-II study, in which the feasibility of the procedure is evaluated proposed and the safety of the product under study, the sample was fixed in 24 patients (12 for each arm of the clinical trial).

5.5 CRITERIA FOR NON-RESPONSE TO TREATMENT

It will be considered that there is no response to treatment if 12 months after the intervention there is no significant clinical changes observed in the questionnaires and / or changes in MRI images showing signs of improvement in dehydration. Shall be deemed the partial response in case of evidence of clinical or regenerative improvement in isolated.

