or contained herniated disc can be considered percutaneous nucleotomy performed under fluoroscopic control, either mechanical, electrothermal or chemical (chymopapain, DiscoGel). Surgical interventions usually have very satisfactory analgesic effects, but are inevitably iatrogenic, reducing mobility and destabilizing neighboring segments, even when these effects are sometimes subclinical (Hilibrand & Robbins, 2004; Harrop et al., 2008; Rihn et al., 2009).

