The interest in preserving the mobility of the affected segment led to the development of prostheses of disk. In the early stages of disc degeneration, nucleus pulposus implants, they can occupy the therapeutic space between discectomy and arthrodesis. Ideally, they are capable of recovering the turgor of the disc, the tension of the fibrous ring and the ability to distribute loads evenly across the disc space. Most designs use viscoelastic polymers that are injected into the disc space (Strange & Oyen, 2012). In Figure 1 we compare the therapeutic efficacy of different procedures in seven recent high-quality clinical trials. Data on the evolution of pain and disability have been calculated and expressed on a scale of 0-100% and the comparison of The treatments have been carried out by comparing the slope of the line that relates relief of the pain versus initial pain (Huskisson, 1974). The slope of the line defines the efficiency of any particular treatment, this maximum being when a slope of 1 (Total relief, Figure 1). Details of the analysis can be found in the publication original (Orozco et al., 2011). Exercise, conventional "non-surgical" treatment plus Common, it was the least potent treatment, with an efficacy of 0.07 (Fritzell et al., 2001). The efficacy of treatments involving cognitive intervention and exercise ranged between 0.20 and 0.29 (Brox et al., 2003; Fairbank et al., 2005; Brox et al., 2006), and the protocols of spinal fusion were the most effective, with an efficacy ranging from 0.30 to 0.71 in different trials (Fritzell et al., 2001; Brox et al., 2003; Fairbank et al., 2005; Hohaus et al., 2008; Guyer et al., 2009). Disc replacement protocols with artificial discs had the same efficacy as fusion alone (Guyer et al., 2009; Siepe et al., 2009). Finally, In one trial, the effects of discectomy were compared to discectomy plus treatment with expanded cells in the excised disc material (ADCT in Figure 1) a small but significant improvement was found in this group, although only after 2 years (Hohaus et al., 2008). This figure also represents the results obtained recently by us with autologous MSVs (Dotted curve marked "This study") (Orozco et al., 2011). The efficacy reached a value of 0.71, a value indistinguishable from the maximums reached with surgical treatments (see discussion in the section next ahead).

2.5. BACKGROUND OF CELLULAR THERAPY.

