5.6 CRITERIA FOR WITHDRAWAL OF PATIENTS AND PROCEDURES TO FOLLOW

Patients can leave the study at any time, without having to give no explanation. Additionally, patients may be withdrawn from the study for the following reasons:

1. They have adverse events that affect participation in the study

2. They do not wish to continue (withdrawal of consent) for any reason.

3. Violation of protocol or significant deviation from specific procedures

of the study

4. Loss of follow-up

5. Appearance of a clinically significant intercurrent disease that affects the participation in the study.

6. The investigator considers that it is beneficial for the patient to withdraw from the study. The withdrawal of the patient from the study will not represent for him any type of damage in the control of their disease, in subsequent treatments or in the treatment to be received by the doctor. If a patient is withdrawn from the study at any time the reason must be recorded in the corresponding sheet of the data collection notebook (CRD). Patients who are withdrawn from the study due to an adverse event or abnormal results of laboratory values should be followed up to total trial resolution or for a period of time considered clinically reasonable by the researcher.

Patients withdrawn from the trial due to an adverse event will be included in security analysis. Patients who have undergone surgically intervened for graft insertion. If a patient is lost, an attempt should be made to contact him. The investigator it should reflect the loss of follow-up in the medical history.

The aim of the study is to obtain 12 evaluable patients in each trial arm (24 in total). A patient will be considered evaluable as long as it has been infiltrated into the space intervertebral a dose of MSV or belongs to the control group. In the event that for some cause the application cannot be made to an included patient, another must be included patient in the same group until reaching the 12 patients treated in each arm of the clinical trial. The study exit and the causes of the study exit of the initial patient and no further follow-up will be necessary since they will not have received the Trial treatment.

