5.8 FOLLOW-UP OF PATIENTS

The research team will inform all patients entering the study of the need to follow a specific periodic control and the importance of going to the planned visits.

To patients who experience adverse events (regardless of whether they have dropped out or withdrawn from the study) will be followed until the incidence has subsided. resolved or stabilized at a level acceptable to both the coordinator and the promoter of the study. As it is a single administration, the option of withdrawal of the medication so it is expected that these patients can continue the follow-up provided in the protocol. All patients included in the study who received cell therapy (including patients who have voluntarily left the study or are withdrawn from it) will continue regular check-ups after participation in the study. These controls will be carried out in the Orthopedic Surgery and Traumatology Service of the Hospital Clínico Universitario de Valladolid with a frequency not less than once a year. These controls should include a clinical evaluation, an X-ray and a general analysis (acceptable if they have been carried out up to 3 months before the visit). The follow-up will be done with a minimum of 5 years. In case that any relevant information was detected for the study related to both the efficacy of the product as well as the safety of the subject (and attributable to the therapy received) is will notify the promoter, initially by telephone and, if deemed appropriate, facilitating supporting documentation (signed report or adverse event form serious) by fax or email.

In addition, and as indicated in the next point, to all patients who have received medication in the study will be given a Participation Card. At this time The research team will ask them that, in case of presenting a health problem relevant inform the doctor who attends you about your participation in said trial clinician by presenting said card. Particular attention will be paid to possibility of histological study if at any time a surgical technique is practiced on the treated area. This follow-up is not required for control patients.

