11.3.7 Efficacy

Changes in pain, disability and quality of life indices will be described in the baseline situation and at 3, 6 and 12 months of treatment, which will be compared as specified in 11.2.

The frequency and percentage of patients presenting signs of regeneration at 12 months of the different interventions, comparing the values as specified in 11.2.

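### Section 5.5 has no rule for disc surgery before month 12, so improvement after an operation is credited to the study injection as at least a partial response

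*Combined protocol and SAP*

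**What the plan says.** **The response rule.** Section 5.5 finds "no response to treatment if 12 months after the intervention there is no significant clinical changes observed in the questionnaires", then joins the absence of MRI improvement with and/or. It adds a middle class: "partial response in case of evidence of clinical or regenerative improvement in isolated". Nothing in 5.5 depends on what happened to the disc between the injection and month 12.

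**Later procedures are foreseen.** Section 5.2.4 says of the pathological study: "It will be carried out obligatorily in case of necessary subsequent intervention on the disc". Section 5.8, on patients who received cells, draws attention to the "possibility of histological study if at any time a surgical technique is practiced on the treated area". Both attach a tissue examination to the event and say nothing about scoring.

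**Expected effect of surgery.** Section 2.4: "Surgical interventions usually have very satisfactory analgesic effects".

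**The analysis.** Section 11.3.7 describes pain, disability and quality of life at baseline "and at 3, 6 and 12 months of treatment, which will be compared as specified in 11.2". It also reports the percentage of patients with signs of regeneration at 12 months. It contains no rule for an intervening procedure.

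**The concern.** Patients enter with pain that has persisted through more than six months of conservative treatment (5.1.1). Section 2.4 describes surgery as the last step for intense, refractory disease. A patient who is operated on at the treated disc during follow-up is a plain case of the injection not having sufficed. If that patient's questionnaires are better at month 12, the rule has no way to see the operation and credits the improvement to the injection.

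Imaging has the same problem. Sections 3.3.1 and 11.2.1.1 take an increase in disc height as a sign of rehydration, and 11.2.1.2 does the same for a rise in the T2 quotient. After an operation at that level, neither measure can be read as an effect of the study treatment.

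The bias can run either way. Operated controls scored as responders shrink the treatment difference. Operated cell-arm patients scored as responders hide failures and inflate it. The doctor who applies the cells is not masked (sections 1 and 4.1), so equal procedure use in the two arms cannot be taken for granted.

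**Working it through.** **1. Applying 5.5 to a patient operated on before month 12.**

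| Questionnaires at month 12 | MRI at month 12 | Class under 5.5 |
|---|---|---|
| improved | improved | response (by implication: neither of the other two classes) |
| improved | not improved | partial response |
| not improved | improved | partial response |
| not improved | not improved | non-response |

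The second row needs care. If and/or means that lack of improvement on either measure is enough for non-response, this patient is a non-responder. But every isolated improvement would then be non-response, and the partial class would be empty. The reading that leaves all three classes usable gives partial response. The wording should be settled in any case.

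**2. Does another section close the gap?**

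- *5.6, withdrawal.* "Additionally, patients may be withdrawn from the study for the following reasons": this is permissive, and a disc procedure is not listed. The listed reasons that could be stretched to cover it depend on judgement.
- *5.8, follow-up.* Patients with adverse events are expected to stay in follow-up, so their month-12 scores would normally exist.
- *6.3, concomitant treatment.* It covers medication, not procedures.
- *11.3.2, efficacy population.* It excludes major protocol violations without defining them.
- *8.4, 11.2.1 and 11.3.6, safety.* An operation requiring hospitalisation could appear among the serious adverse events. The main safety variables count only related ones, and a listing does not alter an efficacy score.

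None of these says how the patient counts for efficacy.

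**3. Weight of one patient.** Section 11.1 fixes 12 per arm on grounds of trial phase, with no effect size or power, so there is no planned figure to reproduce. One reclassified patient moves an arm by 1/12 = 8.3 percentage points. With 11 patients in the per-protocol set it would be 1/11 = 9.1 points.

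**4. How many patients?** The documents give no rate. With an assumed rate q by month 12, the chance of at least one such patient among 24 is 1 − (1 − q)^24:

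| Assumed q | Expected number, 24q | Chance of at least one |
|---|---|---|
| 5% | 1.2 | 71% |
| 10% | 2.4 | 92% |
| 20% | 4.8 | over 99% |

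**5. Effect on a comparison (assumed counts).** Section 11.2 names only the t-test and Wilcoxon test, so a two-sided Fisher exact test is used here for proportions. Suppose 9/12 cell patients and 3/12 controls respond when operated patients count as failures. Now credit k operated controls as responders:

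| k | Control | Difference | p |
|---|---|---|---|
| 0 | 3/12 | 50.0 points | 0.039 |
| 1 | 4/12 | 41.7 points | 0.10 |
| 2 | 5/12 | 33.3 points | 0.21 |
| 3 | 6/12 | 25.0 points | 0.40 |

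In the other direction, a reported 9/12 against 3/12 (p = 0.039) that includes one operated cell patient is really 8/12 against 3/12 (p = 0.10).

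**6. Exclusion is not a cure.** For that last cell arm:

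- crediting the operated patient gives 9/12 = 75.0%;
- dropping the patient gives 8/11 = 72.7%;
- counting the patient as a failure gives 8/12 = 66.7%.

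Exclusion removes the failure from the denominator instead of counting it.

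**The case against.** Several points on the other side are sound and limit the claim.

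- **Partial, not full, response.** A reader might infer that better questionnaires alone make an operated patient a full responder. Section 5.5 does not support that: without MRI improvement the class is partial.
- **The 5.5 classes are not analysed.** Section 11 never names full, partial and non-response as an endpoint. The only efficacy percentage in 11.3.7 concerns regeneration, which pain relief does not change. This stands, so the 8.3 points apply to response under 5.5, or to the regeneration percentage if imaging at an operated level is misread. The questionnaire comparisons are affected separately, through the scores themselves.
- **Surgery and cells are not shown to give equal relief.** Section 2.4 says: "The efficacy reached a value of 0.71, a value indistinguishable from the maximums reached with surgical treatments". A reader might infer that operated patients cannot be told apart from cell responders by score. But 0.71 matches only the surgical maximum (fusion ranges from 0.30 to 0.71), and it comes from autologous cells. It is also the slope of a line relating relief to initial pain across a treatment group, so it cannot be averaged over patients to give a shift in an arm mean. No magnitude on that scale is justified.
- **Timing is not stated.** Section 5.2.4 gives no time frame, and 5.8 speaks of any time within follow-up of at least five years. Procedures before month 12 may be few or none. That bears on size, not on whether a rule is needed.
- **Efficacy is secondary.** Sections 1 and 3.2 make it so in a 24-patient safety and feasibility trial, although 7.1.1 and 11.2.1 list efficacy among the main variables.

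What does not stand is the suggestion that 5.6 or 11.3.2 already deals with these patients. Both leave the decision to be made case by case, possibly after the scores are known.

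**Conclusion.** The concern holds. As written, 5.5 credits a patient operated on at the treated disc before month 12, and improved on the questionnaires afterwards, with at least a partial response to the study injection. The month-12 VAS, Oswestry, SF-12 and imaging comparisons in 11.3.7 are contaminated in the same way.

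The size is 8.3 points per reclassified patient in a full arm of 12, and the direction depends on which arm the patient is in. The number of such patients is unknown; the rates of 5% to 20% and the response counts used above are assumptions. A reader might infer that the efficacy result is certain to be biased, but the documents do not support that: if no one is operated on before V5, nothing changes.

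The plan should be amended, because with arms this small one patient can alter the reading of the comparison. The safety objective is not affected.

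**What to change.** 1. **Section 5.5.** State that any surgery or disc-directed therapeutic procedure at the treated level before V5 is scored as non-response, whatever the later questionnaires or images show. List the qualifying procedures in advance, leaving out diagnostic and analgesic infiltration. Define the level as the affected disc or discs identified at inclusion, so that the rule also works for controls, whose injection is paravertebral. Clarify the and/or wording.
2. **Section 11.3.7.** Count such patients as not showing regeneration at 12 months and keep them in the denominator. Present VAS, Oswestry, SF-12 and the imaging measures as observed, with a sensitivity analysis giving these patients the worst rank after the procedure. The rank test is already among the methods in 11.2.
3. **Data collection.** Add a CRD entry for procedures and their dates in both arms, since 6.3 provides only for medication. Report number and timing by arm.

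The cost is a wording amendment and one CRD field. The small downside is that the response result becomes a composite of outcome and procedure when such events occur. Worst-rank scoring is one of several defensible choices for the continuous scores, which is why it is proposed as sensitivity only. The change concerns scoring, not when such care is given.
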